4.2. Scientific Rationale for Study Design

This 6-week study is the first time a topical PF-07038124 ointment is being evaluated in the AD and psoriasis populations. Previous Pfizer trials in these indications indicate that a 6-week duration is appropriate to assess the efficacy, safety and tolerability. The current nonclinical toxicology package supports the study durations of up to 12 weeks.

For AD the primary endpoint is percent change from baseline in Eczema Area and Severity Index (EASI); secondary endpoints include Investigator's Global Assessment (IGA).

For psoriasis the primary endpoint is percent change from baseline in Psoriasis Area and Severity Index (PASI); the secondary endpoints include Physician Global Assessment (PGA).

Human reproductive safety data are limited for PF-07038124, but there is no suspicion of human teratogenicity based on the intended pharmacology of the compound. In addition, EFD studies conducted in pregnant rats and rabbits at exposures that correspond to 1.7x and 2.7x the maximum planned clinical exposure did not cause any effects on embryo-fetal development. See [Appendix 4](#) for contraceptive requirements.

CCI

4.2.1. Participant Input into Design

Not applicable.

4.3. Justification for Dose

The nonclinical safety profile of PF-07038124 following systemic administration to rats and topical application to minipigs supports human clinical studies of up to 3 months in duration (See [Section 2.2](#)). The dose proposed for this study was determined considering all relevant information obtained from nonclinical safety studies, incorporating the NOAEL from 3-month studies in minipigs, together with the systemic exposure observed following topical application of PF-07038124 to healthy participants. As a result, the dose strength of PF-07038124 selected for this study is 0.01%, applied once daily.

CCI

CCI

4.4. End of Study Definition

A participant is considered to have completed the study if he/she has completed all phases of the study, including the last visit shown in the [SoA](#).

The end of the study is defined as the date of the last visit of the last participant in the study in the trial globally.

5. STUDY POPULATION

This study can fulfill its objectives only if appropriate participants are enrolled. The following eligibility criteria are designed to select participants for whom participation in the study is considered appropriate. All relevant medical and nonmedical conditions should be taken into consideration when deciding whether a particular participant is suitable for this protocol.

Prospective approval of protocol deviations to recruitment and enrollment criteria, also known as protocol waivers or exemptions, is not permitted.

5.1. Inclusion Criteria

The inclusion criteria for AD and psoriasis are overlapping but different. Details of the overlapping inclusion criteria are provided in [Section 5.1.1](#); Disease-specific inclusion criteria are provided in [Section 5.1.2.1](#) and [Section 5.1.2.2](#) for AD and psoriasis respectively.

Participants are eligible to be included in the study only if all of the following criteria apply:

5.1.1. General Inclusion Criteria Applicable for both AD and psoriasis

1. Male or female participants between the ages of 18 and 70 years, inclusive, at Visit 1 (Screening Visit/time of informed consent).
 - Refer to [Appendix 4](#) for reproductive criteria for male ([Section 10.4.1](#)) and female ([Section 10.4.2](#)) participants.
2. Body weight ≥ 50 kg and Body Mass Index (BMI) ≥ 17.5 kg/m² up to 40 kg/m² (inclusive).
3. Capable of giving signed informed consent as described in [Appendix 1](#), which includes compliance with the requirements and restrictions listed in the ICD and in this protocol.
4. Participants who are willing and able to comply with all scheduled visits, treatment plan, laboratory tests, lifestyle considerations, and other study procedures. Refer to [Section 5.3](#) for Lifestyle considerations.

5.1.2. Disease-Specific Inclusion Criteria

5.1.2.1. AD Specific Inclusion Criteria

1. Have been diagnosed with AD for at least 3 months prior to Day 1; the clinical diagnosis of AD will be confirmed according to the criteria of Hanifin and Rajka⁷ ([Appendix 11](#)).
2. Have an Investigator's Global Assessment (IGA) score of 2 (mild), or 3 (moderate) at both the Screening and Day 1/Randomization. Note: Refer to [Section 8.1.2.2](#) for the assessment of 5-point IGA.
3. Have AD covering 5% to 20% (inclusive) of BSA (excluding the scalp) at both the Screening and Day 1/Randomization. Note: Refer to [Section 8.1.2.3](#) for detailed methods of calculating treatable BSA.
4. Have an EASI total score of ≥ 3 to ≤ 21 at Screening and at Day 1/Randomization. Note: Refer to [Section 8.1.2.1](#) for method of calculating EASI scores.
5. Have a Baseline Peak Pruritis Numerical Rating Scale (PP-NRS) average score of ≥ 2 assessed at Day 1/Randomization.

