
 To compare the efficacy of PF-07038124 versus vehicle, using measures of patient reported outcomes (PRO), in participants with mild or 	
 Proportion of participants having ≥ 4 points of reduction in weekly averages of Peak Pruritus Numerical Rating Scale (PP-NRS) from baseline at study visit time points specified in the 	
 Estimand E2: This estimand is intended to provide a population level estimate of the treatment effect of the IP on a binary responder endpoint; without the benefit

ATOPIC DERMATITIS		
Objectives	Endpoints	Estimands
moderate AD.	SoA.	of additional prohibited medications and regardless of a participant compliance with the IP dosing.

 To compare the efficacy of PF-07038124 versus vehicle, on measures of disease and symptom severity in participants with mild or moderate AD. 	
 Change from baseline in EASI total score at study visit time points specified in the SoA. Proportion of participants achieving IGA score of clear (0) or almost clear (1) at study visit time points specified in the SoA. Percent change from baseline in affected Body Surface Area (BSA) at study visit time points specified in the SoA. 	
 All continuous secondary endpoints will be analyzed descriptively and using estimand E1 described above, when appropriate. All categorical secondary endpoints will be analyzed descriptively and using estimand E2 described above, when appropriate.

 To characterize the safety and tolerability of PF-07038124 versus vehicle in participants with mild or moderate AD. 	
 Incidence of treatment emergent adverse events (AEs) and serious adverse events (SAEs), clinically significant changes in vital signs, electrocardiogram (ECG), and laboratory tests. Incidence of severity grades in skin tolerability at times indicated in SoA. 	
 There is no defined estimand for these endpoints and they will be analyzed using Pfizer data standards as applicable.

CCI

CCI

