4. STUDY DESIGN

4.1. Overall Design

This is a phase 2a, randomized, double blind, vehicle controlled, parallel group, multicenter study on the efficacy, safety, tolerability and PK of PF-07038124 0.01% QD versus vehicle control in the treatment of adult participants with mild to moderate AD or mild to moderate plaque psoriasis. In this study the efficacy of PF-07038124 ointment versus vehicle will be assessed in two different indications – there is a separate vehicle control group for each indication.

A total of approximately 88 participants with AD or psoriasis will be randomly assigned to study intervention in this basket trial design.

For AD, a maximum of approximately 56 participants will be randomly assigned to study intervention such that approximately 42 evaluable participants complete the study. Assuming a 25% drop out rate, approximately 28 participants will be randomized to either PF-07038124 or vehicle control to achieve approximately 21 completers in each group. Randomization will be stratified by baseline disease severity (mild [Investigator's Global Assessment or IGA = 2] vs. moderate [IGA = 3]). Up to 25% of AD participants will have an IGA score of 2 at baseline.

For psoriasis, a maximum of approximately 32 participants will be randomly assigned to study intervention such that approximately 24 evaluable participants complete the study. Assuming a 25% drop out rate, approximately 16 participants will be randomized to PF-07038124 or vehicle control to achieve 12 completers in each group. Randomization will be stratified by baseline disease severity (mild [Physician Global Assessment or PGA = 2] vs. moderate [PGA = 3]). Up to 25% of participants will have a PGA score of 2 at baseline.

The total duration of study participation will be approximately 17 weeks, including a screening period of up to 6 weeks, a double-blind, placebo-controlled treatment period of 6 weeks, and a safety follow-up period of 4-5 weeks from last dose of study drug to last study visit. The study intervention arms and duration for AD and psoriasis participants are the same (See [Section 1.1](#) for detailed Study Intervention Groups and [Section 1.2](#) for Study Schema).

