8.1.3.1. Peak Pruritus Numerical Rating Scale (PP-NRS) for AD

The PP-NRS is a daily patient-reported assessment of intensity of pruritus on an 11-point numerical rating scale, ranging from 0 ('No Itch') to 10 ('Worst Itch Imaginable') with a 24-hour recall period.² The PP-NRS will be completed once daily at least 7 days prior to Day 1, and completed once daily every day from Day 1 to Week 6 before IP dose is applied preferably at the same time of each day if applicable, as noted in the [SoA](#). Note that PP-NRS will be assessed daily during the 7 days immediately preceding randomization and a minimum of 4 daily scores out of the 7 days prior to Day 1 is required to calculate the baseline average score.

CCI

CCI

EFFICACY ASSESSMENTS FOR PSORIASIS

All efficacy assessments of psoriatic skin will be based only on areas treated with IP and excluding scalp, palms, soles, nails from the assessment/scoring.

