9. STATISTICAL CONSIDERATIONS

Detailed methodology for summary and statistical analyses of the data collected in this study is outlined here and further detailed in a SAP, which will be maintained by the sponsor. The SAP may modify what is outlined in the protocol where appropriate; however, any major modifications of the primary endpoint definitions or their analyses will also be reflected in a protocol amendment.

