9.1. Estimands and Statistical Hypotheses

9.1.1. Estimands for AD

The primary estimand will be the population average treatment effect on percent change from baseline in EASI score relative to vehicle at 6 weeks in the absence of prohibited medication without regard to compliance. All observations after the initiation of prohibited medication will be set to missing. Missing data from all causes, including post-randomization prohibited medication use will be imputed in the PF-07038124 arms using a copy to control method (ie, missing data in 0.01% QD regimen will be imputed from the distribution of participants on QD vehicle). Participants with inadequate compliance will have their recorded EASI scores used as is in the analysis. The population-based treatment effect will be the differences in the mean change from baseline in treatment arm compared to the vehicle.

The secondary estimand will be the estimated population average treatment effect on the rates of IGA response (participants with a score of 0 or 1 and a 2 point or greater decrease from baseline) at Week 6 relative to vehicle without regard to compliance with IP in the absence of prohibited medication. This is a composite estimand where success is defined as achievement of an IGA response as defined above while remaining on study, providing data and not taking prohibited medication; lack of compliance or adverse events will not be counted as a failure. The population-based treatment effect will be the differences in the proportions of success in each treatment arm compared to the corresponding vehicle. EASI 75 and other EASI scores will be treated in a similar manner.

All other secondary continuous clinical endpoints will be analyzed using the primary estimand, while all other secondary categorical clinical endpoints will be analyzed using the secondary estimand described above. CCI

Other estimands may be used for some of the primary and secondary endpoints as a means to examine the robustness of the results and to compare to available literature as needed. Details of these analyses will be presented in the Statistical Analysis Plan (SAP).

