9.2. Sample Size Determination

9.2.1. Sample Size Determination for AD

The sample size calculation is based on the primary endpoint (percentage change from baseline in EASI score at Week 6). A total of 56 randomized participants in 1 treatment group and 1 vehicle group (28/arm) will provide approximately 90% power to detect a difference of 50 in percentage change from baseline with a common standard deviation 48% between PF-07038124 and a vehicle arm, controlling the two-sided error rate alpha 0.05. These calculations allow for a 25% dropout rate leaving 42 evaluable participants (21/arm).

For the key secondary endpoint, IGA response rate of clear or almost clear and ≥ 2 points improvement at Week 6, assuming 20% rate for vehicle and 55% rate for the treatment, this sample size provides 66% power controlling the two-sided error rate alpha 0.05.

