9.4.1. Efficacy Analyses for AD

Endpoint	Statistical Analysis Methods
Primary: Percent Change from Baseline EASI at Week 6	A landmark analysis using analysis of covariance of percent change from baseline in EASI, adjusting for the baseline EASI score, to estimate the effect of the initially randomized treatment in the absence of prohibited medication regardless of treatment compliance. The analysis will use the mITT analysis set. Missing data due to any cause including censoring due to initiation of prohibited medication will be imputed using the corresponding vehicle arm, missing data in a vehicle arm will be imputed using data from the vehicle arm assuming data are missing at random (MAR). The analysis will combine the results from the multiple imputations using Rubin's rule as implemented in SAS PROC MIANALYZE.
Secondary: IGA Response at Week 6	A landmark analysis of the composite endpoint; achieving IGA without prohibited medication, while remaining on study and providing data. The analysis will use the mITT analysis set. Based on the definition of the composite endpoint all participants in the mITT set will have a response for all visits (ie, there is no missing data). The proportions responding and

Endpoint	Statistical Analysis Methods
	the corresponding risk difference comparing active treatment arm to vehicle group will be analyzed using the unconditional exact method; the risk differences and the corresponding 2-sided unconditional exact 90% confidence intervals will be computed using Chan and Zhang (1999) ¹⁶ method.

CCI

Other continuous secondary endpoints at time points specified in the SoA including change from baseline EASI, will be analyzed as described for the primary estimand along with descriptive statistics and possibly graphical displays.

Other binary secondary endpoints at time points specified in the SoA including, CCI EASI 75, CCI IGA of clear or almost clear will be analyzed as described for the secondary estimand along with descriptive statistics and possibly graphical displays.

CCI

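### A 4-point PP-NRS response is impossible for AD participants who enter with baseline itch below 4, and no visible analysis or by-arm count separates them out

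*Protocol*

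**What the plan says.** - **Entry.** Protocol 5.1.2.1 item 5 requires a baseline PP-NRS "average score of ≥ 2 assessed at Day 1/Randomization".
- **Scale.** Protocol 8.1.3.1 describes an "11-point numerical rating scale, ranging from 0" (no itch) to 10 (worst itch). SAP 3.4 takes baseline as the mean of the Day -7 to Day -1 scores, so it need not be a whole number.
- **Endpoint.** Protocol 3.1 and SAP 3.2 define response as at least 4 "points of reduction in weekly averages of Peak Pruritus Numerical Rating Scale (PP-NRS) from baseline at study visit time points specified in the" Schedule of Activities.
- **Analysis.** Protocol 9.1.1 states that "all other secondary categorical clinical endpoints will be analyzed using the secondary estimand described above". For the IGA response that serves as the model, Protocol 9.4.1 says: "Based on the definition of the composite endpoint all participants in the mITT set will have a response for all visits". SAP 6.2.2 handles PP-NRS response in the same way as IGA response: mITT, a Chan and Zhang risk difference and a 90% interval. Under SAP 5.3.1, missing values count as non-response unless due to COVID-19. mITT (SAP 4) is everyone randomised and dosed, with no condition on baseline itch.
- **Subsets.** SAP 6.5, which is not redacted, plans none.
- **Balance.** Protocol 4.1: "Randomization will be stratified by baseline disease severity", which for AD means IGA 2 versus 3. Itch is not a stratification factor.

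**The concern.** The entry threshold is 2 points lower than the change that counts as success. A participant who enters between 2 and just under 4 and becomes itch-free is scored as a failure at every visit, on drug or vehicle.

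Two things follow. First, a low response rate could mean a weak effect on itch or a sample in which many could not qualify, and no visible output tells these apart. Second, with 28 per arm and no stratification on itch, the number unable to respond may differ between arms by chance without the report showing it.

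This is the only patient-reported responder endpoint visible for AD, so it is where a reader will look for the itch effect.

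**Working it through.** **1. The plan's own figures.** No power is stated for PP-NRS response. The only binary AD endpoint with a stated power is IGA response (Protocol 9.2.1: 20% versus 55%, two-sided 0.05, 66%). With 21 evaluable per arm and the pooled normal approximation:

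- null SE = √(2 × 0.375 × 0.625 / 21) = 0.1494
- alternative SE = √((0.20 × 0.80 + 0.55 × 0.45) / 21) = 0.1393
- power = Φ((0.35 − 1.96 × 0.1494) / 0.1393) = Φ(0.41) = 65.9%

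The stated 66% is reproduced. No stated figure is in dispute here.

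**2. The ceiling.** The largest possible fall equals the baseline minus 0. For 2 ≤ baseline < 4 the fall is below 4, so response is impossible. At exactly 4, response needs a weekly average of 0.

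**3. Dilution.** Let s be the share with baseline below 4, equal in both arms, and p the response rate among those able to respond. The all-mITT rate is p(1 − s), and the risk difference also shrinks by (1 − s). The documents give neither s nor p, so the values below are assumptions: s from 10 to 40%, p = 50% on drug and 20% on vehicle, 28 per arm. Half-widths are 1.645 × SE (Wald), using n = 28(1 − s) for the restricted set.

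| s | Unable per arm (28s) | Reported difference (30 × (1 − s)) | 90% half-width, all mITT | 90% half-width, baseline ≥ 4 |
|---|---|---|---|---|
| 10% | 2.8 | 27 | 19.5 | 21.0 |
| 20% | 5.6 | 24 | 19.0 | 22.3 |
| 30% | 8.4 | 21 | 18.3 | 23.8 |
| 40% | 11.2 | 18 | 17.5 | 25.7 |

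Example at s = 10%: √((0.45 × 0.55 + 0.18 × 0.82) / 28) = 0.119, and × 1.645 = 19.5 points. Restricted: √((0.25 + 0.16) / 25.2) = 0.128, and × 1.645 = 21.0 points.

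**4. Chance imbalance.** Treat the numbers unable to respond as two independent binomial(28, s) counts. The probability that they differ by 4 or more is 0.115, 0.240, 0.307 and 0.340 for s = 10, 20, 30 and 40%. An excess of 4 in one arm lowers that arm's rate by 4/28 × 20% = 2.9 points if 20% of those able respond, and by 4/28 × 50% = 7.1 points if 50% do.

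**5. Power.** Unconditional exact pooled-z test, 0.05 in the upper tail, restricted n per arm binomial(28, 1 − s). Entries are all mITT versus restricted, in %.

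| Rates among those able | s = 10% | 20% | 30% | 40% |
|---|---|---|---|---|
| 50 v 20 | 68.2 v 70.8 | 62.0 v 66.1 | 55.1 v 60.5 | 47.6 v 53.8 |
| 37.5 v 15 | 53.3 v 53.8 | 47.6 v 49.8 | 41.8 v 45.3 | 36.0 v 39.9 |
| 30 v 10 | 51.7 v 51.7 | 46.3 v 48.0 | 40.8 v 43.6 | 35.4 v 38.3 |
| 40 v 20 | 42.0 v 43.0 | 37.5 v 39.6 | 32.8 v 35.9 | 28.2 v 31.5 |
| 60 v 30 | 62.8 v 67.0 | 55.2 v 62.6 | 48.4 v 57.0 | 42.0 v 50.5 |

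The second row is the first after 25% dropout scored as non-response (50 × 0.75 and 20 × 0.75). Restriction gains between 0 and 9 points of power, so power is not the main reason to change.

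**The case against.** The strongest reply is that nothing is wrong with the planned analysis. SAP 2.1.2 defines the E2 population by the entry criteria, the all-mITT difference is unbiased for it, and type I error is not inflated. SAP 5.1 confines formal inference to the primary endpoints. All of that stands, which is why the planned analysis should stay as it is.

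Other points also stand in part:

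- **The interval already covers chance imbalance.** Variation in who can respond is part of the binomial variation in each arm's rate. The 7.1-point shift is smaller than one standard error of the difference (10.6 to 11.9 points at 50 v 20). Imbalance is therefore a matter of explanation, not of validity. Any link between IGA and itch would make it smaller than computed.
- **Baseline itch may be summarised.** SAP 5.2.2 and the open-ended list in SAP 6.6.1 could both yield baseline PP-NRS by arm. They would give means, medians and ranges, not the number below 4.
- **Redaction.** Redacted blocks adjoin several relevant sections, so a further itch analysis could be hidden. The claim is limited to visible text, although the unredacted SAP 6.5 excludes subset analyses.
- **The count might be enough.** Nobody below 4 can respond, so responders divided by those at or above 4 gives the restricted rate. The count is indeed the more valuable half of the change. The pre-specified analysis adds the exact interval and avoids a restriction chosen after seeing results.

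**Conclusion.** The concern holds. The ceiling follows by arithmetic from the entry criterion, the scale and the endpoint, and needs no assumption. The visible plan has no analysis or by-arm count that separates participants who did not respond from those who could not.

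The consequence is dilution and a harder interpretation, not bias. Its size depends on a share below 4 that the documents do not give. For equal shares of 10 to 40%, an assumed 30-point effect is reported as 27 to 18 points. If the shares differ between arms, the simple (1 − s) scaling of the difference no longer applies, and the estimate can move either way.

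One secondary endpoint is affected; the primary EASI analysis is not. The change is worth making before unblinding because it is cheap and the same restriction chosen later would look data-driven.

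**What to change.** Keep the all-mITT E2 analysis as the main analysis. Add to SAP 6.2.2, with a cross-reference in 6.5 and a row in Appendix 1:

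> *The number and percentage of participants with baseline weekly average PP-NRS (Day -7 to Day -1) below 4 will be reported by arm. The 4-point PP-NRS response will also be analysed, by the same method, in mITT participants with a baseline of at least 4.*

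The restriction uses a value fixed before dosing, so the comparison remains randomised. If the sponsor prefers the restricted set as the main analysis, SAP 2.1.2 should state the change of population and note the departure from Protocol 9.1.1 and 9.4.1. Protocol 9 permits this: "The SAP may modify what is outlined in the protocol where appropriate".

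**Cost.** Three short edits, no new data, and no change to entry criteria or the planned analysis. It adds one secondary result that describes only participants with baseline itch of at least 4, with a wider interval (half-width 21.0 to 25.7 points instead of 19.5 to 17.5 at 50 v 20). The cut-off of 4 is only the arithmetic minimum: a participant just above it still needs near-complete clearance of itch to respond.
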